6 PARTICIPANT ELIGIBILITY

Investigators are responsible for confirming participant eligibility and will be required to maintain a log that includes limited information about all screened participants (e.g., initials, age, sex; as allowed per local regulations) and outcome of screening.

6.1 Inclusion Criteria

For inclusion in the trial the participant must fulfill ALL of the following criteria:

- 6.1.1 Male or female 18 to 55 years of age at the time of signing the ICF.
- 6.1.2 Willing and able to give informed consent for participation in the trial.
- BMI of 18 to 40 kg/m² inclusive and a body weight \geq 50 kg at screening. 6.1.3
- 6.1.4 Diagnostic and Statistical Manual of Mental Disorders (DSM-5) diagnosis of schizophrenia, confirmed by the Mini-International Neuropsychiatric Interview (MINI) for Psychotic Disorders Studies.
- 6.1.5 Clinically stable outpatient, based on the investigator's judgment and defined by no signs of exacerbation of schizophrenia (no hospital admissions or prison incarcerations), and no evidence of an increased level of psychiatric care (including cognitive behavior rehabilitation or individual psychotherapy) within 12 weeks prior to screening.
- 6.1.6 PANSS-T score of \geq 60 and \leq 110 at screening and baseline visits.
- Score of ≥ 4 for at least 2 of the following PANSS items: delusions (P1), 6.1.7 conceptual disorganization (P2), hallucinatory behavior (P3), suspiciousness (P6), somatic concern (G1), or unusual thought content (G9) at screening visit.
- 6.1.8 Score ≥ 4 (at least moderately ill) on the CGI-S at screening visit.
- 6.1.9 Undergoing treatment with at least 1 antipsychotic medication with no change in dosing, supported by documentation (including pharmacy records), for at least 8 weeks prior to screening and no change in antipsychotic medication dosing planned throughout the trial.
- 6.1.10 Taking a maximum of 2 antipsychotic medications. For participants taking oral antipsychotic medications only, the sum of primary and secondary antipsychotic medications is ≤ 30 mg/day of oral olanzapine equivalents. For participants taking long-acting injectable antipsychotic medications, the dose is within the range approved and any secondary oral antipsychotic medications is ≤ 5 mg/day of oral olanzapine equivalents.

Study Code: GWAP19030

EudraCT Number: 2019-003369-16 Clinical Protocol Global V3, 23Mar2021

6.1.11 Documented response (at least partially) to treatment with current antipsychotic medications (e.g., treatment of recent exacerbation of psychotic symptoms) as assessed by the investigator or treating physician. Documentation can include medical records, pharmacy records, or corroboration in writing by the clinician(s) currently responsible for the participant's psychiatric treatment.

- 6.1.12 On a stable dose if taking concomitant psychotropic medications and within allowed limits, including antidepressants, anxiolytics, anticholinergics and/or antiepileptics for at least 4 weeks prior to screening (dose reductions ≤ 25% of total dose are permitted) with no plans to change dosing during the trial (i.e., from screening onwards). Valproic acid or any prescribed valproate product (valproate semisodium or valproate sodium) is disallowed within 4 weeks (i.e., more than 5 half-lives) prior to the baseline visit.
- 6.1.13 Willing to allow the responsible authorities to be notified of participation in the trial, if mandated by local law.

6.2 Exclusion Criteria

The participant may not enter the trial if ANY of the following apply:

Diagnosis and Psychiatric History

- 6.2.1 Recent (within the last 3 months prior to screening) diagnosis of panic disorder, depressive episode, or other comorbid psychiatric conditions based on the MINI for Psychotic Disorders Studies (or DSM-5) **OR** has PANSS item G6 score of ≥ 5 (depression) at screening.
- 6.2.2 Any psychiatric disorder that may interfere with the conduct of this trial, including but not limited to attention deficit hyperactivity disorder, pervasive developmental disorder, intellectual disability, personality disorder that might interfere with compliance or increase suicidal risk, manic or hypomanic episode, or any other psychotic disorder, as defined in the DSM-5.
- 6.2.3 Current diagnosis or a history of substance use disorder according to DSM-5 criteria within 6 months prior to screening or prior chronic substance abuse judged likely to recur during the trial period by the investigator. Nicotine use or occasional cannabis use (≤ 3 days per week recreational cannabis use) is acceptable. Corroboration of the participant's frequency of cannabis use by an adult informant (e.g., family member,

EudraCT Number: 2019-003369-16 Clinical Protocol Global V3, 23Mar2021

- social worker, caseworker, residential facility staff, or nurse) should be obtained if the participant has a positive urine test for THC at screening.
- 6.2.4 A positive drug screen for opiates, methadone, cocaine, amphetamines (including ecstasy), or barbiturates; a repeat drug screen may be done to verify the result.
- 6.2.5 Any history of suicidal behavior or any suicidal ideation of type 4 or 5 on the adult C-SSRS within 1 month prior to screening.
- 6.2.6 A $\pm \ge 20\%$ change in PANSS-T score during the placebo run-in period (Visit 2 to Visit 3).

Treatment History

- 6.2.7 Treatment-resistant schizophrenia as judged by the treating physician and as defined by having previously demonstrated no response to > 2 trials of antipsychotic trial medications at therapeutic doses or required clozapine therapy due to non-response to antipsychotic therapy within the previous 6 months.
- 6.2.8 Non-compliance, as assessed by antipsychotic medication and the IMP adherence monitoring Platform:
 - ≤ 75% compliance of current oral antipsychotic medication during the single-blind, placebo run-in periods (Visit 2 to Visit 3).
 - ≤ 75% compliance of current long-acting injectable antipsychotic medication as assessed by number of administrations falling more than 1 week outside of the scheduled due date of administration, in the 6 months prior to screening (Visit 1) and baseline (Visit 3).
 - ≤ 75% compliance of IMP during the single-blind, placebo run-in period (Visit 2 to Visit 3) for current IMP.
- 6.2.9 Based on the investigator assessment;
 - current antipsychotic medication blood levels are below the therapeutic range if therapeutic drug monitoring is available for the antipsychotic(s) prescribed for the participant; or
 - there is no documentation confirming the administration of long-acting injectable antipsychotic medication within the approved dose range and as prescribed by the treating physician.

Past and Current Medical History

Study Code: GWAP19030

EudraCT Number: 2019-003369-16 Clinical Protocol Global V3, 23Mar2021

- 6.2.10 History of moderate or severe head trauma (for example, loss of consciousness for more than 15 minutes) or other neurological disorders (including epilepsy), neurodegenerative disorder (Alzheimer's disease, Parkinson's disease, multiple sclerosis, Huntington's disease, etc.) or systemic medical diseases that are, in the opinion of the investigator, likely to interfere with the conduct of the trial or confound the trial assessments.
- 6.2.11 Tardive dyskinesia (TD) that is moderate to severe (i.e., a score of > 21 on the dyskinesia subscale of the ESRS at screening) or requires treatment.
- 6.2.12 Any other significant disease, disorder, pending court proceedings or social circumstances (e.g., homelessness) which, in the opinion of the investigator, may either put the participant, other participants, or site staff at risk because of participation in the trial, may influence the result of the trial, or may affect the participant's ability to take part in the trial.

Other

- 6.2.13 Any known or suspected hypersensitivity to cannabinoids or any of the excipients of the IMP, such as sesame seed oil.
- 6.2.14 One or more laboratory values outside the normal range, based on the blood or urine samples taken at the screening visit, that are considered by the investigator to be clinically significant; or the participant has impaired hepatic function at screening, defined as serum alanine aminotransferase (ALT) or aspartate aminotransferase (AST) > 2 × upper limit of normal (ULN) or total bilirubin (TBL) > 1.5 × ULN or international normalized ratio (INR) > 1.2 (TBL ULN parameter not applicable for participants diagnosed with Gilbert's disease). Note: Out-of-range laboratory values should be confirmed on retest within the allowed screening window.
- 6.2.15 Clinically relevant abnormalities in the ECG measured at screening or randomization (including QT interval with Fridericia correction [QTcF] > 450 msec for males and > 470 msec for females, average of 3 measurements).
- 6.2.16 Positive serology panel (including hepatitis B surface antigen [HBsAg] and/or confirmed current hepatitis C infection [positive hepatitis C virus {HCV} antibody confirmed with reflex HCV RNA test]) and/or positive human immunodeficiency virus (HIV) antibody/p24 antigen screens.

Study Code: GWAP19030

EudraCT Number: 2019-003369-16 Clinical Protocol Global V3, 23Mar2021

- 6.2.17 Male and fertile (i.e., after puberty unless permanently sterile by bilateral orchidectomy) and with a partner of childbearing potential unless agree to ensure that they use male contraception (e.g., condom) or remain sexually abstinent during the trial and for 3 months after the last dose.
- 6.2.18 Female of childbearing potential (i.e., following menarche until becoming postmenopausal for ≥ 12 consecutive months unless permanently sterile by hysterectomy, bilateral salpingectomy, or bilateral oophorectomy) unless agree to use highly effective contraception (e.g., combined [estrogen and progestogen containing] hormonal contraception associated with inhibition of ovulation [oral, intravaginal or transdermal], progestogen-only hormonal contraception associated with inhibition of ovulation [oral, injectable or implantable], intrauterine devices/hormone-releasing systems, bilateral tubal occlusion, vasectomized partner [provided partner is the sole sexual partner and has received medical assessment of the surgical success], true sexual abstinence) during the trial (i.e., from screening) and for 3 months after the last dose.
- 6.2.19 Female who is pregnant (positive pregnancy test), lactating, or planning pregnancy during the trial or within 12 weeks after the last dose.
- 6.2.20 Received an IMP within 12 weeks prior to the screening visit.
- 6.2.21 Donated blood within 12 weeks prior to the screening visit and is unwilling to abstain from donation of blood during the trial.
- 6.2.22 Previously randomized into the placebo run-in period of this trial.
- 6.2.23 Travel outside the country of residence planned during the trial, unless the participant has confirmation that the IMP is permitted in the destination country.
- 6.2.24 Currently using or within 3 months of screening has used CBD oil or purified CBD preparations and is unwilling to abstain for the duration of the trial.

Study Code: GWAP19030 EudraCT Number: 2019-003369-16

Clinical Protocol Global V3, 23Mar2021

7 PARTICIPANT ENROLMENT

Before participants enter the trial, GW requires a copy of the relevant site's institutional review board (IRB) or independent ethics committee (IEC) written approval of the protocol, ICF, and other participant information material. Participants will be considered enrolled in the trial from the time of providing written informed consent. All participants must personally sign and date the consent form prior to any procedures being performed (refer to Section 15.2).

7.1 **Treatment Assignment**

At the start of Visit 1, enrolled participants will be allocated a unique participant number. After completion of assessments and confirmation of eligibility at Visit 2, participants will be assigned a unique treatment number and will be randomized 1:1 to receive 150 mg b.i.d. or 500 mg b.i.d. dose matched volumes of placebo in a single-blind manner for the placebo run-in period. At Visit 3 (Day 1) participants who continue to meet the required eligibility criteria will be randomized 2:1 to receive GWP42003-P or placebo of equivalent volume to their placebo run-in allocation (Table 7.1-1) in a double-blind manner for the treatment period. GW will provide all IMP in a packed and labelled state and the RTSM system will identify the pack number to be dispensed to the participant at each relevant visit, according to the treatment assigned in the randomization schedule.

Table 7.1-1 Participant Treatment Assignment					
Single-blind Allocation (Run-in Period)	Double-blind Allocation (Treatment Period)				
150 mg b.i.d. placebo	150 mg b.i.d. GWP42003-P				
	150 mg b.i.d. placebo				
500 mg b.i.d. placebo	500 mg b.i.d. GWP42003-P				
	500 mg b.i.d. placebo				

b.i.d. = twice daily.

7.2 Randomization

The allocation of IMP to treatment number will be done according to a randomization schedule produced by an independent statistician. The assignment during the placebo run-in period will be single-blinded and assignment during the treatment period will be double-blinded. The randomization schedule will be held centrally and not divulged to any other person involved in the trial until the database has been locked and unblinding authorized by the relevant GW personnel. For access to blinded treatment assignment, see Section 8.5.

EudraCT Number: 2019-003369-16 Clinical Protocol Global V3, 23Mar2021

8 TREATMENT PROCEDURES

8.1 Investigational Medicinal Product Dosage, Administration, and Schedule

The IMP will be presented as an oral solution containing 100 mg/mL GWP42003-P or only excipients (in the case of placebo). For details regarding IMP formulations, see Section 5.

8.1.1 Dose Administration

IMP will be self-administered orally (swallowed) b.i.d. (e.g., morning and evening) preferably within 30 minutes of a meal using the syringe(s) provided. The IMP may be taken with other concomitant medications, as directed by the investigator. During the PK visits, the participants' morning dose of IMP will be administered at the trial site following predose PK blood draws, with a standardized meal of at least 300 kcal under the supervision of site staff. Staff should observe dosing and provide feedback on correct dosing methods if necessary.

8.2 Concomitant Therapy

Participants will be taking at least 1 antipsychotic medication, or a maximum of 2 antipsychotic medications. For participants taking oral antipsychotic medications only, the sum of primary and secondary antipsychotic medication is ≤ 30 mg/day of oral olanzapine equivalents. For participants taking long-acting injectable antipsychotic medications, the dose is within the range approved and any and secondary oral antipsychotic medications is ≤ 5 mg/day of oral olanzapine equivalents.

Concomitant psychotropic medications including antidepressants, anxiolytics, anticholinergics, and/or antiepileptics are allowed provided that the current dose has been unchanged for the 4 weeks prior to screening (dose reductions permitted) with no plans to change dosing during the trial (i.e., from screening onwards).

Any medication, other than the IMP, taken during the trial must be recorded in the electronic case report form (eCRF).

8.3 Prohibited Therapy During Trial Period

The following medications are prohibited for the duration of the trial beginning from the date of the screening visit. If applicable, the possible effects of these medications on the efficacy endpoints will be considered during the assessment of the evaluable period.

Cannabis or THC-based products within 24 hours prior to Visits 1, 3, and 7.

Clinical Protocol Global V2 Based on Clinical Protocol V1 11Nov2019

EudraCT Number: 2019-003369-16 Clinical Protocol Global V3, 23Mar2021

• Valproic acid or any prescribed valproate product (valproate semisodium or valproate sodium) and psychostimulants taken within 4 weeks (i.e., more than 5 half-lives) prior to the baseline visit.

• Clozapine taken within 6 months prior to screening.

The following medications are restricted for the duration of the trial beginning from the date of the screening visit until the completion of assessments at Visit 7 or the discontinuation visit:

- Daily doses of anticholinergic drugs for the treatment of extrapyramidal side effects will be limited to 1 mg/day or less of benztropine or biperiden or 2 mg/day or less of trihexyphenidyl or equivalents.
- Daily doses of benzodiazepine receptor agonists will be limited to 2 mg/day or less of lorazepam or equivalents. Benzodiazepines will be prohibited within 24 hours prior to Visits 1, 3, and 7.
- Daily doses of hypnotics will be limited to 10 mg/day of zolpidem or zopiclone or 3 mg/day of eszopiclone. Hypnotics will be prohibited within 24 hours prior to Visits 1, 3, and 7.
- Daily doses of tricyclic antidepressants will be limited to 100 mg/day or less of amitriptyline or equivalents.
- Lithium, tricyclics, and other psychotropic medications that may affect cognition should be discussed with sponsor prior to enrolling the participant.

8.4 Compliance in Investigational Medicinal Product Administration

Refer to Appendix 1 for when IMP will be dispensed. Further guidance on IMP dispensing will be provided in a separate pharmacy manual.

Please see Section 5.3.5 for details on the IMP adherence and reminder system.

Participants should return all IMP (used and unused) at each relevant visit (Appendix 1), and participants must return placebo IMP from the placebo run-in period before randomization to the treatment period. The IMP will be checked, and any discrepancies discussed with the participant at the time of the visit and documented accordingly within the participant's source documents.

The investigator must inform GW promptly of all missing or unaccountable IMP.

Records of IMP accountability will be maintained according to Section 5.3.4.

EudraCT Number: 2019-003369-16 Clinical Protocol Global V3, 23Mar2021

In cases where participants are not able to attend trial visits due to special circumstances (e.g., Coronavirus disease 2019 [COVID-19] pandemic), the investigator will discuss with the sponsor potential mitigation approaches for IMP dispensing, secure delivery, and collection.

8.5 Access to Blinded Treatment Assignment

The identity of IMP assigned to participants will be held by the RTSM system. The principal investigator (PI) at each site, or his/her designee, is responsible for ensuring that information on how to access the RTSM system for an individual participant is available to the relevant staff in case of an emergency and unblinding is required. A participant's treatment assignment should only be unblinded when knowledge of the treatment is essential to decide on the medical management of the participant. Unblinding for any other reason will be considered a protocol deviation.

The investigator is encouraged to contact GW to discuss the rationale for unblinding prior to doing so. However, to prevent delays to the investigator or medical personnel responding to a potentially emergent situation, unblinding of IMP will not be dependent upon the investigator receiving approval from GW (i.e., the investigator will be able to obtain the code break information independent of contacting GW).

If the investigator does unblind, they must contact GW within 1 working day of the event and must document the time, date, and reason(s) for unblinding in the participant's medical notes and on the eCRF.

Confidential Page 50 of 104
Clinical Protocol Template (Phase 2–4)

Study Code: GWAP19030 EudraCT Number: 2019-003369-16 Clinical Protocol Global V3, 23Mar2021

9 TRIAL PROCEDURES

A list of the required trial procedures is provided in the schedule of assessments (Appendix 1). Assessments or tests that are not completed and examinations that were not conducted must be reported on the electronic eCRF.

Participants will be issued with the participant information and ICF. Following adequate time to discuss the trial with the investigator, nurse or relatives, participants who provide written informed consent will be screened for entry into the trial.

The location of the source data for the trial procedures (Appendix 1) will be documented, per site, in a signed source data verification plan; for further details see Section 16.2.

9.1 Trial Procedures

9.1.1 Informed Consent

All participants with an adequate level of understanding must personally sign and date the IRB/IEC-approved ICF before any trial-specific procedures are performed or any participant-related data are recorded for the trial. For participants with an insufficient level of understanding of what is proposed, only parent(s)/legal representative consent will be sought. If an adult participant is unable to read (illiterate or visually impaired), or is physically unable to speak or write, an impartial witness should be present during the entire informed consent discussion. After the ICF is read and explained to the participant and after the participant has orally consented to participation in the trial and has signed and dated the ICF (if capable of doing so), the witness should also sign and personally date the ICF. By signing the ICF, the witness attests that the information in the ICF was accurately explained to and apparently understood by the participant and that informed consent was freely given by the participant.

If the participant cannot write, they can give consent by "making their mark" on the consent form (e.g., writing an "X").

Informed consent should be taken in accordance with the guidance provided in ICH E6 by an appropriately trained and delegated site staff member. A physician should be available to answer any questions from the participant. The original signed ICF should be retained and a copy provided to the participant. Participants will be given the option of being informed about the summary outcome and results of the trial as part of the ICF. For further details, see Section 15.2.

EudraCT Number: 2019-003369-16 Clinical Protocol Global V3, 23Mar2021

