15.2 Informed Consent

An initial master ICF will be prepared by GW and provided to the investigator, who will tailor this for their site by adding the site's contact details and by using headed paper. The GW clinical manager will communicate updates to the template by letter. The written informed consent document should be prepared in the language(s) of the potential participant population.

Before a participant's involvement in the trial, the investigator or authorized delegate is responsible for obtaining written informed consent from the participant after adequate explanation of the aims, methods, anticipated benefits and potential hazards of the trial and before any trial-specific procedures are performed or any participant-related data are recorded for the trial. The participant must have ample time to consider the information provided before giving written consent. More specific definitions of 'ample time' may be in force if required by IRBs/IECs or local regulations.

The acquisition of informed consent must be documented in the participant's medical records and the ICF must be signed and personally dated by the participant and by the person who conducted the informed consent discussion. Informed consent should be taken in accordance with the guidance provided in ICH E6 by an appropriately trained and delegated site staff member. A physician should be available to answer any questions from the participant should they arise. The original signed ICF should be retained and a copy provided to the participant.

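### Protocol Section 9.1.1 provides a representative-only consent route that contradicts inclusion 6.1.2, Section 7 and Section 15.2

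*Protocol*

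**What the plan says.** The protocol covers consent in several places.

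- **Section 9.1.1** ties the personal signature to comprehension: "All participants with an adequate level of understanding must personally sign and date the IRB/IEC-approved ICF before any trial-specific procedures are performed". For everyone else it says: "For participants with an insufficient level of understanding of what is proposed, only parent(s)/legal representative consent will be sought". It mentions no assent from the participant. It then describes an impartial-witness procedure for adults who cannot read, or who are physically unable to speak or write, and refers to Section 15.2 for more detail.
- **Section 6.1**: "For inclusion in the trial the participant must fulfill ALL of the following criteria". Criterion 6.1.2 is "Willing and able to give informed consent for participation in the trial". The synopsis repeats it.
- **Section 7**: "All participants must personally sign and date the consent form prior to any procedures being performed". There is no exception.
- **Section 15.2**: the investigator or delegate is "responsible for obtaining written informed consent from the participant after adequate explanation", and "the ICF must be signed and personally dated by the participant and by the person who conducted the informed consent discussion". No parent or legal representative appears in this section.
- **Section 9 (opening text) and Definition of Terms**: screening follows the participant's own written consent, and a participant counts as enrolled once he or she has given it.

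**The concern.** A site member taking consent from someone who does not understand the trial finds two instructions. Section 9.1.1 says to obtain the representative's consent and nothing from the participant. Section 7 says no procedure may start until the participant has signed personally. Section 9.1.1 is the working instruction for that staff member, and the reference onward to 15.2 does not help, because 15.2 describes no representative process.

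At stake is the protection of people who cannot consent for themselves. If 9.1.1 is followed, such a person could undergo screening procedures without the signature that Section 7 makes a precondition. The provided sections do not define who may act as representative, whether assent is needed, or whether consent is sought again if understanding returns.

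**Working it through.** No arithmetic applies, and the protocol gives no figure to reproduce. The check sets the passages side by side and asks whether any reading satisfies all of them.

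**Step 1. Does the scope differ?** Section 7 speaks of all participants. Section 9.1.1 splits participants into those who understand and those who do not, and requires the personal signature only of the first group.

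| Person lacks understanding of the trial | What the section requires |
|---|---|
| 9.1.1 | Consent of parent or legal representative only |
| 6.1.2 | Person fails inclusion |
| 7 | Person must sign before any procedure |
| 15.2 | Consent obtained from, and form signed by, the participant |

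For this person, 9.1.1 cannot be followed together with 7 or 15.2.

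**Step 2. Does the witness text resolve it?** No. It deals with problems of reading, speech or writing. The witness attests that the participant appeared to understand and agreed freely, so the procedure presupposes the understanding that is missing here.

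**Step 3. Does 6.1.2 resolve it?** Only in part. Section 9.1.1 sits under trial procedures and Section 6.1 governs entry. All inclusion criteria are mandatory and nothing exempts a represented person from 6.1.2, so that person remains ineligible. But consent comes before eligibility review. Appendix 1 places physical examination, ECG, chemistry, hematology, serology, PK blood sampling and the MINI at Visit 1. Its note on eligibility review says the forms go to the clinical surveillance and training (CST) review after the diagnostic process and screening assessments are complete. A later screen failure would not undo procedures already performed.

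**Step 4. How many people?** The documents do not report how consent was obtained for anyone. SAP Section 3.2 says the trial stopped early with 80 participants randomized of 366 planned (80 / 366 = 21.9%, given there as 22%). It does not give the number screened. The number consented by a representative only is therefore unknown and may be zero.

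**Step 5. Would deleting text from 9.1.1 alone give agreement?** Not completely. The retained witness text asks for the participant's signature only where the participant can give it, while Sections 7 and 15.2 state the signature rule without exception. The witness exception has to appear in all three sections.

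**The case against.** The strongest reply is that 6.1.2 already keeps these people out, so the sentence in 9.1.1 has no effect. A reader might infer from 9.1.1 that the protocol admits people who cannot consent, or that sites have two competing entry rules. The documents do not support that: 9.1.1 sets a consent procedure and entry is decided by Section 6.1. This part of the reply stands. It does not remove the conflict with Sections 7 and 15.2, or the exposure at Visit 1.

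A reader might also infer that ineligible people were randomized. That would require 6.1.2 to be disregarded, the CST review to miss it, and the eligibility checks at Visits 2 and 3 to miss it as well. Nothing in the documents suggests that this happened.

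A third inference is that the required PANSS scores make incapacity likely. The protocol draws no such link. The population is clinically stable outpatients (6.1.5) with a documented, at least partial, response to current treatment (6.1.11), and 6.2.2 excludes intellectual disability and other psychiatric disorders that may interfere with trial conduct. The symptom criterion 6.1.7 can be met without delusions, hallucinations or conceptual disorganization.

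Finally, whether representative consent would be legally valid cannot be judged from these documents, and the consent form itself is not available for review. The finding concerns only the protocol's agreement with itself. The reference to parents in a trial of adults aged 18 to 55 suggests leftover template wording, but that is an inference.

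**Conclusion.** The contradiction is real and no other section resolves it. It is an internal inconsistency in the consent rule, and its realistic consequence is limited to Visit 1 procedures performed on a representative's consent alone. Its size in people is unknown and may be zero. No sample size, power figure, endpoint or analysis depends on it, so it should be corrected but does not call the trial's results into question. The conclusion rests on reading the sections as written and on Section 6.1 governing entry. The stronger claims, that 9.1.1 overrides 6.1.2 or that ineligible people were randomized, are not supported.

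**What to change.** Reconcile the passages as follows.

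1. In Section 9.1.1, delete the sentence that provides for representative-only consent, and delete from the preceding sentence the qualifier that restricts personal signature to those who understand. Section 9.1.1 then agrees with 6.1.2, 7 and 15.2 on who consents.
2. Keep the impartial-witness procedure. State it in 9.1.1, 7 and 15.2 as the only exception to the personal-signature rule, for participants who understand the trial and give their own agreement under that procedure but cannot read, speak or write.
3. Because the trial has terminated early, check the consent records of all screened and randomized participants for any case consented by a representative only, and report each such case as a deviation.

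The cost is a wording change in three sections and one review of consent records. Adults who cannot consent for themselves become clearly ineligible, which 6.1.2 already provides. If the sponsor did intend a representative route, the deletion would not be the right edit: 6.1.2, 7 and 15.2 would have to be amended and the missing safeguards written.
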